10.2. Ethical Review

Lilly or its representatives must approve all ICFs before they are used at investigative sites(s). All ICFs must be compliant with the International Conference on Harmonisation (ICH) guideline on GCP.

The investigator must give assurance that the ERB was properly constituted and convened as required by ICH guidelines and other applicable laws and regulations.

Documentation of ERB approval of the protocol and the ICF must be provided to Lilly before the study may begin at the investigative site(s). The ERB(s) will review the protocol as required.

The study site's ERB(s) should be provided with the following:

- the current IBs and updates during the course of the study
- ICF
- relevant curricula vitae

10.3. Regulatory Considerations

This study will be conducted in accordance with:

- 1) consensus ethics principles derived from international ethics guidelines, including the Declaration of Helsinki and Council for International Organizations of Medical Sciences (CIOMS) International Ethical Guidelines
- 2) the ICH GCP Guideline [E6]
- 3) applicable laws and regulations

The investigator or designee will promptly submit the protocol to applicable ERB(s).

Some of the obligations of the Sponsor will be assigned to a third-party organization.

An identification code assigned to each patient will be used in lieu of the patient's name to protect the patient's identity when reporting AEs and/or other trial-related data.

10.4. Investigator Information

Physicians with a specialty in oncology will participate as investigators in this clinical trial.

10.5. Protocol Signatures

The Sponsor's responsible medical officer will approve the protocol, confirming that, to the best of his or her knowledge, the protocol accurately describes the planned design and conduct of the study.

After reading the protocol, each principal investigator will sign the protocol signature page and send a copy of the signed page to a Lilly representative.

10.6. Final Report Signature

The clinical study report coordinating investigator will sign the final clinical study report for this study, indicating agreement that, to the best of his or her knowledge, the report accurately describes the conduct and results of the study. The coordinating investigator will be the investigator with the most enrolled patients; if this investigator is unable to fulfill this function, another investigator will be chosen by the Sponsor.

The Sponsor's responsible medical officer and statistician will approve the final clinical study report for this study, confirming that, to the best of his or her knowledge, the report accurately describes the conduct and results of the study.

10.7. Complaint Handling

Lilly collects product complaints on investigational products and drug delivery systems used in clinical studies in order to ensure the safety of study participants, monitor quality, and to facilitate process and product improvements.

Complaints related to unblinded concomitant drugs are reported directly to the manufacturers of those drugs/devices in accordance with the package insert.

The investigator or his/her designee is responsible for handling the following aspects of the product complaint process in accordance with the instructions provided for this study:

- recording a complete description of the product complaint reported and any associated AEs using the study-specific complaint forms provided for this purpose
- faxing the completed product complaint form within 24 hours to Lilly or its designee

If the investigator is asked to return the product for investigation, he/she will return a copy of the product complaint form with the product.

10.8. Data Quality Assurance

To ensure accurate, complete, and reliable data, Lilly or its representatives will do the following:

- provide instructional material to the study sites, as appropriate
- sponsor start-up training to instruct the investigators and study coordinators. This training will give instruction on the protocol, the completion of the CRFs, and study procedures.
- make periodic visits to the study site
- be available for consultation and stay in contact with the study site personnel by mail, telephone, and/or fax
- review and evaluate CRF data and use standard computer edits to detect errors in data collection
- conduct a quality review of the database

In addition, Lilly or its representatives will periodically check a sample of the patient data recorded against source documents at the study site. The study may be audited by Lilly or its representatives, and/or regulatory agencies at any time. Investigators will be given notice before an audit occurs.

To ensure the safety of participants in the study, and to ensure accurate, complete, and reliable data, the investigator will keep records of laboratory tests, clinical notes, and patient medical records in the patient files as original source documents for the study. If requested, the investigator will provide the sponsor, applicable regulatory agencies, and applicable ERBs with direct access to original source documents.

10.8.1. Data Capture System

An electronic data capture system will be used in this study. The site maintains a separate source for the data entered by the site into the Sponsor-provided electronic data capture system.

Case report form data will be encoded and stored in a clinical trial database.

Data from complaint forms submitted to Lilly will be encoded and stored in the global product complaint management system.

10.9. Study and Site Closure

10.9.1. Discontinuation of Study Sites

Study site participation may be discontinued if the Sponsor, the investigator, or the ERB of the study site judges it necessary for medical, safety, regulatory, or other reasons consistent with applicable laws, regulations, and GCP.

Attachment 1. Protocol JVDF Time and Events Tables

Time and Events Table: Baseline, Study Treatment, and Postdiscontinuation Follow-Up Periods

	Study Period						Notes
	Baseline (within 28 days prior to enrollment)			Treatment (21-day cycles) ±7 days		Postdiscontinuation Follow-Up	
Procedure	≤28 days	≤21 days	≤7 days	Day 1	Day8	Short-Term Follow-Up Visit (30 ±7 days)	Long-Term Follow-Up Visit (every 90 ±7 days)
Informed consent form (ICF)	X						Obtain ICF prior to any study-specific procedures. If the ICF is revised during the course of the study, re-consenting of patients may be required if deemed necessary by Lilly or the ERB.
Inclusion/exclusion criteria	X						
Medical history	X						Including preexisting conditions and historical illnesses
ECG	X				X		Baseline, short-term follow-up, and when clinically indicated
Echocardiogram or MUGA scan	X						Baseline, and when clinically indicated
ECOG Performance Status	X			X		X	A time window of -3 days of Day 1 is permitted for the ECOG assessment.
Brain Scan	X						Baseline brain scan by CT or MRI for NSCLC patients and Urothelial patients only. Refer to eligibility criteria.
Concomitant therapy	X			X		X	Concomitant medications will be recorded, including any taken within 30 days prior to enrollment and those taken during the 30 days after the last dose of study treatment.
Physical exam	X			X		X	A time window of ±3 days with respect to the other study visit procedures is permitted.

	Study Period						Notes	
	Baseline (within 28 days prior to enrollment)			Treatment (21-day cycles)		Postdiscontinuation Follow-Up		
Procedure	≤28 days	≤21 days	≤7 days	Day 1	Day 8	Short-Term Follow-Up Visit (30 ±7 days)	Long-Term Follow-Up Visit (every 90 ±7 days)	Day 8 procedures are only for Cohort A, A1, and A2 (Gastric-GEJ or BTC Ram 8 mg/kg, Days 1 and 8). Long-term follow-up should be attempted at regularly scheduled intervals (every 90 days [±7 days]) until death, loss to follow-up, or study completion (whichever occurs first).
Height, weight	X			X				Measure height at baseline only. Measure weight at the beginning of each cycle. Recalculate the ramucirumab dose if weight change is ≥10% compared to previous measurement(s).
Vital signs	X			X	X			For the first 2 ramucirumab infusions, measure blood pressure and pulse as follows: (i) within 15 minutes prior; (ii) after infusion completion; and (iii) at the end of the 1-hr post-infusion observation period. Measure blood pressure and pulse prior to each subsequent ramucirumab infusion. Measure other vital signs as clinically indicated.
AE collection; CTCAE grading	X							During short-term follow-up, all AEs/SAEs will be collected. At the 90-day long-term follow-up visit, all SAEs will be collected. Thereafter, during long-term follow-up, only SAEs that are related to study regimen or protocol procedures will be collected.

	Study Period						Notes
	Baseline (within 28 days prior to enrollment)			Treatment (21-day cycles)		Postdiscontinuation Follow-Up	
Procedure	≤28 days	≤21 days	≤7 days	Day 1	Day 8	Short-Term Follow-Up Visit (30 ±7 days)	Long-Term Follow-Up Visit (every 90 ±7 days)
Laboratory Assessment							
Hematology	X			X		X	Local only. Within 3 days prior to Day 1 of each cycle.
Chemistry	X			X		X	Local and central: Local chemistry laboratory testing will be used to determine patient eligibility and decisions for treatment. Central chemistry laboratory testing will be used for subsequent scheduled analyses. Within 3 days prior to Day 1 of each cycle.
Urinalysis	X			X		X	Local only. Within 3 days prior to Day 1 of each cycle. 24-hr urine protein analysis if urine protein is ≥2+ at baseline, >2+ during study treatment.
T3, free T4, TSH	X			X		X	Central and local as needed. At baseline, within 3 days prior to Day 1 of Cycle 3, Day 1 of Cycle 6, and every 2 cycles thereafter; and more frequently if clinically indicated.
Coagulation	X			X		X	Local only. Within 3 days prior to Day 1 of every odd-numbered cycle.
Pregnancy test			X			X	Local only. Required for women of child-bearing potential. If required per local regulations and/or institutional guidelines, testing can occur at other times during the study treatment period.

	Study Period						Notes
	Baseline (within 28 days prior to enrollment)		Treatment (21-day cycles)		Postdiscontinuation Follow-Up		
Procedure	≤28 days	≤21 days	≤7 days	Day 1	Day 8	Short-Term Follow-Up Visit (30 ±7 days)	Long-Term Follow-Up Visit (every 90 ±7 days)
Efficacy Assessment							
Tumor imaging and assessment		X		X	X	X	Assessments previously obtained as part of routine clinical care may be used as the baseline assessment if performed within 21 days prior to enrollment. Imaging is not required on Cycle 1 Day 1. SEE FOOTNOTE.
Survival information					X	X	Follow-up for the collection of survival data and subsequent anticancer treatments should be attempted at regularly scheduled intervals (every 90 days [±7 days]) for up to 2 years after patients receive the first dose. This follow-up might be a phone call to the patient, her/his family, or local doctor.
Additional Analyses							
Tumor tissue	X						New biopsy at baseline (recent to Cycle 1 Day 1) is required. For first line NSCLC, PD-L1 >=1% is required. Tumor tissue collection during the treatment period is optional, and can be provided if available, for example in case of a clinically-indicated biopsy.
Genetics Whole Blood Sample			X				Collect 1 sample prior to treatment on Cycle 1 Day 1.
• Biomarker • Pharmacokinetics • Immunogenicity	See Attachment 2 .						

	Study Period						Notes	
	Baseline (within 28 days prior to enrollment)			Treatment (21-day cycles)		Postdiscontinuation Follow-Up		
Procedure	≤28 days	≤21 days	≤7 days	Day 1	Day 8	Short-Term Follow-Up Visit (30 ±7 days)	Long-Term Follow-Up Visit (every 90 ±7 days)	The first study treatment will be administered within 7 days following enrollment. Postdiscontinuation follow-up begins when the decision is made that the patient will no longer continue study treatment.
Administration of Study Drugs								Day 8 procedures are only for Cohort A, A1, and A2 (Gastric-GEJ or BTC Ram 8 mg/kg, Days 1 and 8). Long-term follow-up should be attempted at regularly scheduled intervals (every 90 days [±7 days]) until death, loss to follow-up, or study completion (whichever occurs first).
Administer Ramucirumab								Administer ramucirumab first per the dose schedule to which the patient is allocated. For first 2 cycles, implement a 1-hr observation period i) between ramucirumab and pembrolizumab administration, and ii) after pembrolizumab infusion. For all cycles thereafter, no observation period will be required unless clinically indicated.
BTC 8 mg/kg				X	X			
Gastric-GEJ 8 mg/kg				X	X			
Gastric-GEJ 10 mg/kg				X				
NSCLC 10 mg/kg				X				
Urothelial 10 mg/kg				X				
Administer Pembrolizumab								
200 mg fixed				X				

Time and Events Table (concluded)

Abbreviations: AE = adverse event; Att. = attachment; BTC = biliary tract cancer; CT = computed tomography; CTCAE = Common Terminology Criteria for Adverse Events; ECG = electrocardiogram; ECOG PS = Eastern Cooperative Oncology Group performance status; ERB = ethical review board; Gastric-GEJ= Gastric-Gastroesophageal Junction; ICF = informed consent form; MRI = magnetic resonance imaging; MUGA = multiple-gated acquisition; NSCLC = non-small cell lung cancer; PD = progressive disease; Prot. Ref. = protocol reference; Ram = ramucirumab; SAE= serious adverse event; TSH = thyroid-stimulating hormone.

FOOTNOTES Regarding Tumor Assessment:

- During treatment cycles, perform tumor assessment and imaging as follows: (i) every 6 weeks (± 7 days) for the first 6 months after enrollment, and (ii) every 12 weeks (± 7 days) thereafter. Perform as scheduled even if study treatment is delayed, except when tumor assessment and imaging are not feasible in the opinion of the investigator because of the patient's clinical status.
- If radiologic imaging verifies initial progressive disease (PD), tumor assessment should be repeated approximately 4 weeks later in order to confirm PD with the option of continuing study treatment while awaiting radiologic confirmation of progression (Section 8.1.1.3).
- During the short-term and long-term follow-up periods, for patients who discontinue study treatment without objectively measured PD, continue to perform tumor assessment and imaging every 6 to 12 weeks depending on standard of care.

Time and Events Table: Continued Access Period

	Continued Access Period			Notes
	Continued Access Treatment (21-day cycles)	Continued Access	Follow-Up	
				Day 1 and Day 8 assessments are performed only if study drug dosing is scheduled to occur on that day. Continued access follow-up begins 1 day after the patient and the investigator agree that the patient will no longer continue treatment in the continued access period and lasts approximately 30 days. Efficacy assessments will be performed at the investigator's discretion based on the standard of care.
Relative Day within a Cycle	Day 1	Day 8		
Procedures				
Weight	X			
Administer Ramucirumab				
BTC 8 mg/kg	X	X		
Gastric-GEJ 8 mg/kg	X	X		
Gastric-GEJ 10 mg/kg	X			
NSCLC 10 mg/kg	X			
Urothelial 10 mg/kg	X			
Administer Pembrolizumab 200 mg (fixed)				
All treatment cohorts	X			
AE Collection, CTCAE Grading	X	X	X	Data on SAEs that occur before the end of trial will be stored in the collection database and the Lilly Safety System. After the patient is no longer participating in the study (that is, no longer receiving study treatment and no longer in follow-up), only SAEs that the investigator is made aware of and are related to study regimen or protocol procedures will be collected.
Immunogenicity and PK Sample				If a patient experiences an IRR to ramucirumab, blood samples for immunogenicity and PK analysis will be taken at the following time points: (1) as soon as possible after the onset of the IRR, (2) at the resolution of the IRR, and (3) 30 days after the IRR.

Abbreviations: AE = adverse event; BTC = biliary tract cancer; CTCAE = Common Terminology Criteria for Adverse Events; GEJ = gastroesophageal junction; IRR = infusion-related reaction; NSCLC = non-small cell lung cancer; PK = pharmacokinetics; SAE =serious adverse events.

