1.b.	Infusion-related reaction	3-4	Immediately and permanently discontinue ramucirumab
2.	Hypertension		
2.a.	Hypertension (non-life-threatening and associated with symptoms) NOTE: Hypertension should be monitored prior to each ramucirumab infusion.	3	
 • Delay ramucirumab until the hypertension is controlled with medication and is resolved to Grade 0-2. 
 ◦ If controlled with medication and resolved to Grade 0-2, then may resume ramucirumab at current dose. ◦ If NOT controlled with medication and not resolved to Grade 0-2 within a reasonable timeframe, discontinue ramucirumab at investigator's discretion.
2.b.	Uncontrolled hypertension, hypertensive crisis, or hypertensive encephalopathy	4	Immediately and permanently discontinue ramucirumab.

Dose-Modification Guidelines for Ramucirumab for Adverse Events at least Possibly Related to Ramucirumab, including Adverse Events of Special Interest (continued)

	Adverse Event NOTE: All Specific Adverse Events Listed are defined as AESIs in Section 8.2.1.1.1.	CTCAE Grade	Dose-Modification Guidelines NOTE: Dose reductions to occur as defined in Table JVDF.3.
3.	Proteinuria		
3.a.	Proteinuria = 2+ (dipstick or routine urinalysis) ^a		
 Administer ramucirumab at the current dose if clinically indicated. Obtain 24-hour urine protein results within 3 days prior to the next ramucirumab dose. 
 If urine protein is <2 g/24 h, administer ramucirumab at the patient's current dose. If urine protein is ≥2 g/24 h, modify the ramucirumab dose based on 24-hour collection. See Proteinuria ≥2 g/24 h (24-hour urine collection), Line 3.c in this table.
3.b.	Proteinuria >2+ (dipstick or routine urinalysis) ^a		
 Delay ramucirumab until urine protein returns to <2 g/24 h. Obtain 24-hour urine protein results within 3 days prior to the next ramucirumab dose. 
 If urine protein is <2 g/24 h, no further dose delay or dose reduction is required. If urine protein remains ≥2 g/24 h and is not resolved within a reasonable timeframe, discontinue ramucirumab at investigator's discretion.

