13.b	Adverse Event	4	
Permanently discontinue treatment immediately, with the exception of Grade 4 fever or Grade 4 laboratory abnormality, in which case:
 
 • First occurrence: Delay ramucirumab until resolved to Grade 0-1. 
 ◦ If resolved to Grade 0-1, may resume ramucirumab original dose at the discretion of the investigator. ◦ If NOT resolved to Grade 0-1 within a reasonable timeframe, discontinue ramucirumab at investigator's discretion. • Second occurrence: Delay ramucirumab until resolved to Grade 0-1. 
 ◦ If resolved to Grade 0-1, reduce ramucirumab dose. ◦ If NOT resolved to Grade 0-1 within a reasonable timeframe, discontinue ramucirumab at investigator's discretion.

Dose-Modification Guidelines for Ramucirumab for Adverse Events at least Possibly Related to Ramucirumab, including Adverse Events of Special Interest (concluded)

Abbreviations: AESI = adverse event of special interest; CTCAE = Common Terminology Criteria for Adverse Events; NCI = National Cancer Institute.

- a Perform urinalysis within 3 days prior to each infusion of ramucirumab. If 24-hour urine collection is also performed, the results of 24-hour urine collection should be used for clinical decision-making.
- b Patients who enter the study with symptoms or laboratory values equivalent to NCI-CTCAE Version 4.0 Grade 1-2 adverse events should not necessarily have dose delays or reductions related to the persistence or mild worsening of those symptoms or laboratory values. Grade 2 toxicities which represent clinically significant worsening of symptoms from baseline, ramucirumab dose may be delayed at the discretion of the investigator. If the toxicity is resolved to Grade 0-1, may reduce ramucirumab dose. If the toxicity is not resolved to Grade 0-1, may discontinue ramucirumab.

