8.2. Safety

Investigators are responsible for monitoring the safety of patients who have entered this study and for alerting Lilly or its designee to any event that seems unusual, even if this event may be considered an unanticipated benefit to the patient.

The investigator is responsible for the appropriate medical care of patients during the study.

The investigator remains responsible for following, through an appropriate health care option, AEs that are serious, considered related to the study, or that caused the patient to discontinue before completing the study. The patient should be followed until the event is resolved or explained. Frequency of follow-up evaluation is left to the discretion of the investigator.

The timing of all safety evaluations is shown in the Time and Events Table ([Attachment 1](#)).

[Table JVDF.7](#) presents a summary of AE and SAE reporting guidelines and shows which database or storage system is used.

Table JVDF.7. Adverse Event and Serious Adverse Event Reporting Guidelines

Period	Types of AEs/SAEs to be Reported^a	Collection Database^b	Lilly Safety System
Baseline (pretreatment)	Preexisting conditions	x	X
	All AEs	x	
	SAEs related to protocol procedures	x	
Study treatment period	All AEs	x	X
	All SAEs	x	
Short-term postdiscontinuation follow-up (30 days)	All AEs	x	X
	All SAEs	x	
Long-term postdiscontinuation period			
Through post-discontinuation follow-up visit (90 days)	All SAEs	x	X
Additional long-term discontinuation follow up (every 90 days to study completion)	All SAEs related to protocol procedures or IP	x	X
Continued access period	All AEs	x	X
	All SAEs	x	
Continued access follow-up (30 days; or sooner, to occur when patient begins a new anti-cancer therapy)	All AEs	x	X
	All SAEs	x	
After the patient is no longer participating in the study (that is, no longer receiving study treatment and no longer in follow-up)	All SAEs related to protocol procedures or IP that the investigator becomes aware of		X

Abbreviations: AEs = adverse events; CRF = case report form; IP = Investigational Product (ramucirumab or pembrolizumab); SAEs = serious adverse events.

a Although not strictly adverse events, pregnancy and breastfeeding are reported as SAEs. The reporting period starts after receiving IP(s) and ends 120 days after discontinuing study treatment or 30 days following cessation of treatment if the patient initiates new anticancer therapy, whichever is earlier.

b CRF collection guidelines will be followed.

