Attachment 3. Protocol JVDF Clinical Laboratory Tests

Hematology-Local only	Clinical Chemistry-Local and Central^a
Hemoglobin	Serum Concentrations of:
Hematocrit	Sodium
Erythrocyte count (RBC)	Magnesium
Leukocytes (WBC)	Potassium
Absolute Neutrophil Count	Total bilirubin
Lymphocytes	Direct bilirubin (if total bilirubin is above ULN)
Monocytes	Alkaline phosphatase
Eosinophils	Alanine aminotransferase (ALT)
Basophils	Aspartate aminotransferase (AST)
Platelets	Blood urea nitrogen (BUN)
	Creatinine
	Uric acid
	Calcium
	Glucose, random
	Albumin
	Cholesterol
	Creatine kinase (CK)
	Chloride
	Total protein
	Phosphorus
	Lactate dehydrogenase (LDH)
	Pregnancy Test Urine or Serum^c-Local Only
	β-human chorionic gonadotropin (β-hCG)
Coagulation Test^d Local Only	
Prothrombin time (PT) /INR	
Partial thromboplastin time (PTT) or activated PTT (aPTT)	

Abbreviations: INR= International Normalized Ratio; RBC = red blood cells; ULN = upper limit of normal;

WBC = white blood cells.

- a. Local chemistry laboratory testing will be used to determine patient eligibility and decisions for treatment. Central chemistry laboratory testing will be used for subsequent scheduled analyses.
- b. A microscopic exam is required for abnormal results. If urinalysis indicates proteinuria $\geq 2+$ at baseline or during the treatment period, a 24 hour urine collection (to assess protein) must be obtained.
- c. Minimum sensitivity 25 IU/L or equivalent units of β-human chorionic gonadotropin (β-HCG), for women of childbearing potential (WOCBP). If urine pregnancy results cannot be confirmed as negative, a serum pregnancy test will be required.
- d. For both prothrombin time and partial thromboplastin time, the laboratory for each is selected at baseline, and should be followed during the study period.

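### The Attachment 1 urinalysis row omits the test before Schedule 1 Day 8 ramucirumab and sets a looser on-treatment trigger for 24-hour urine than Table JVDF.4 and Attachment 3

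*Protocol*

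**What the plan says.** Three places in the protocol govern urine protein monitoring on treatment.

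- **Attachment 1, Laboratory Assessment, Urinalysis.** The row is marked at Day 1 and not at Day 8. Its note reads "Within 3 days prior to Day 1 of each cycle. 24-hr urine protein analysis", and the trigger for that analysis is 2+ or more at baseline but ">2+ during study treatment". Section 8.2 sends sites to this table: "The timing of all safety evaluations is shown in the Time and Events Table".
- **Table JVDF.4 (Section 6.6.1).** Footnote a says "Perform urinalysis within 3 days prior to each infusion of ramucirumab". Line 3.a, headed "Proteinuria = 2+ (dipstick or routine urinalysis"), states "Administer ramucirumab at the current dose if clinically indicated", and requires the 24-hour result "within 3 days prior to the next ramucirumab dose".
- **Attachment 3, footnote b.** For a urinalysis showing 2+ or more "at baseline or during the treatment period, a 24 hour urine collection (to assess protein) must be obtained".

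Table JVDF.2 gives Schedule 1 ramucirumab on Day 1 and Day 8 of each 21-day cycle, and Schedule 2 on Day 1 only.

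**The concern.** A site working from the schedule it has been told to use can give Day 8 ramucirumab without the urinalysis that the dosing table requires. It can also leave a 2+ dipstick on treatment without a 24-hour collection.

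These results drive dosing. Above 2+ on dipstick, line 3.b holds ramucirumab. At 2 g/24 h or more, line 3.c requires a hold, then a dose reduction on recovery. Above 3 g/24 h, line 3.d and Section 6.9.1.2.1.2 require permanent discontinuation. A test that is not done cannot trigger any of these.

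Safety and tolerability of the two regimens is the primary objective. The timing gap falls only on Schedule 1, the more intensive one: the SAP (Section 5.2.1.2) gives planned ramucirumab intensities of 5.3 and 3.3 mg/kg/week. Sites that follow different parts of the protocol would also apply the dose-modification rules differently.

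**Working it through.** There is no stated figure to reproduce. The check is a comparison of texts plus day counts.

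**Timing**

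Inputs: urinalysis 0 to 3 days before Day 1 (Attachment 1); limit of 3 days before each infusion (Table JVDF.4 footnote a); Schedule 1 infusions on Days 1 and 8 (Table JVDF.2).

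- Interval from Day 1 to Day 8: 8 − 1 = 7 days.
- Age of the result at Day 8: 7 + 0 = 7 to 7 + 3 = 10 days.
- Excess over the limit: 7 − 3 = 4 to 10 − 3 = 7 days.

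So the scheduled test cannot cover a nominal Day 8 infusion, and 1 of 2 infusions per Schedule 1 cycle has none tied to it. Planned patients: 15 (Cohort A) + 25 (A1) + 25 (A2) = 65 in Phase 1b, plus up to 6 DLT-evaluable patients in Phase 1a Schedule 1. Schedule 2 is unaffected, because its only infusion is on Day 1.

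The first block of Attachment 1 has ±7 days in the treatment header. If that window is assumed to apply to the Day 8 visit with Day 1 held fixed, the interval is 7 ± 7 = 0 to 14 days and the age is 0 to 14 + 3 = 17 days. A sample taken on Day 1 itself meets the 3-day limit only up to Day 4 (1 + 3). The conclusion does not depend on this range.

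The blank Day 8 cell is not the main evidence, since columns may have shifted when the table was read. The ECG mark, for instance, sits under Day 8 while its note refers to short-term follow-up. The urinalysis note itself names Day 1 only. By contrast, the vital signs row carries a Day 8 mark and a note tied to each ramucirumab infusion, so the table uses per-infusion wording elsewhere.

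**Trigger for 24-hour urine**

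| Urinalysis result | Attachment 1 | Table JVDF.4 | Attachment 3 |
|---|---|---|---|
| 2+ or more, baseline | required | not addressed | required |
| exactly 2+, on treatment | not required | required (3.a) | required |
| above 2+, on treatment | required | required (3.b) | required |

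The conflict is confined to exactly 2+ on treatment, in any cohort. Line 3.a still permits the current dose, so what is missed is the result due before the next one. After a Day 1 result of 2+, that result falls due nominally on Days 5 to 8 in Schedule 1 (next dose Day 8) and Days 19 to 22 in Schedule 2 (next dose Day 22).

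**The case against.** The strongest reply is that the safeguards are already in the protocol. Footnote a, line 3.a and Attachment 3 all remain in force, and Attachment 1 forbids none of them, so a site that cross-checks can comply with every text. That is true and limits the severity. It does not remove the conflict, because Section 8.2 names Attachment 1 as the source for timing, and its different triggers at baseline and on treatment look deliberate.

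A second reply is that footnote a is attached only to the proteinuria lines of an adverse-event table, so it might mean closer monitoring once proteinuria has appeared, with Attachment 1 giving the routine schedule. Hematology and chemistry are also timed to Day 1 only. This reading is possible but strained: the footnote carries no such condition and refers to each infusion. Even if it were accepted, the trigger conflict would remain.

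Third, the clinical consequence is not quantified. Section 6.9.1.2.1.2 says most proteinuria events in ramucirumab trials were Grade 1 or 2, and a later result above 2+ triggers the 24-hour test under every text. This stands. The lower end of the 0 to 17 day range is also unrealistic, since it would put both 8 mg/kg doses on one day.

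**Conclusion.** Both inconsistencies are real, and nothing in the protocol or SAP resolves them. The timing gap affects one of two ramucirumab infusions in every Schedule 1 cycle; the nominal result is 4 to 7 days past the 3-day limit. This rests on nominal visit days and on reading footnote a as written. The trigger gap affects any patient with exactly 2+ on treatment.

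The documents give no frequency for 2+ results, so neither the number of patients affected nor the number of Day 8 doses that would change can be estimated. No effect on efficacy estimates, sample size or power is claimed. The protocol should be corrected, as a matter of safety monitoring and consistent dosing; the validity of the trial is not threatened.

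**What to change.** In Attachment 1:

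- Mark urinalysis at Day 8 for Schedule 1 (Cohorts A, A1, A2 and the Phase 1a Schedule 1 patients).
- Reword the note so that the local urinalysis falls in the 3 days before every ramucirumab infusion, and a 24-hour collection follows any result of 2+ or higher, at baseline or on treatment.

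Two additions would help. The note could point to line 3.a for when the 24-hour result is due. The sponsor should also state what applies in continued access, where the schedule gives Day 1 and Day 8 ramucirumab but has no urinalysis row.

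The cost is an edit to one table row and one dipstick per Schedule 1 cycle at a visit that already takes place (at most 35 per patient over the 35-cycle maximum). The extra 24-hour collections are already required by Table JVDF.4 and Attachment 3. Some Day 8 doses may be held as a result, which is what the dosing rules intend.
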